9.2.2.1. Alternative LRTI / Severe LRTI case definitions for data analysis in infants

To meet an alternative case definition, a participant must have at least one item from each column.

Note: As per protocol amendment 5, the alternative case definitions will no longer be considered for data analysis in infants.

Table 13 Alternative LRTI / Severe LRTI case definitions in infants

	RSV confirmed	Documented PE findings indicating lower respiratory tract involvement	Objective measures of clinical severity
LRTI	Confirmed RSV infection	Rhonchi Crackles (Rales) Wheeze	Increased respiratory rate (bpm)
			
 • ≥ 60 for < 2 mo • ≥ 50 for 2-6 mo
			Hypoxemia
			
 • SpO2 <95% at ≤1800 meters • SpO2 <92% at > 1800 meters
			New onset apnea
			Nasal flaring
Retractions			
Grunting			
Severe LRTI	Confirmed RSV infection	Rhonchi Crackles (Rales) Wheeze	Hypoxemia
			
 • SpO2 <93% at ≤1800 meters • SpO2 <90% at > 1800 meters
			Acute hypoxic or ventilatory failure
			Dehydration due to respiratory distress requiring IV hydration
			Failure to respond or unconscious

9.2.3. Hematology and Biochemistry parameters

In order to assess the impact of fluid shifts on the antibody concentration/titer, hematocrit will be evaluated at all three blood sampling timepoints (Day 1, Day 31, and delivery) for a subset of maternal (Stage A) participants in the immunogenicity sub-cohort, if deemed necessary.

Note that hematocrit sample collection will end once Protocol Amendment 2 becomes effective in the different countries/sites.

9.3. Statistical Method

Study Specific statistical methods for immunogenicity analysis are described in section [5.3](#).

10. ANNEXES

10.1. Business rules for standard data derivations and statistical methods

This section contains GSK Vaccines' standard rules for data display and derivation for clinical and epidemiological studies. These rules will be applied along with those detailed in section [9](#) (additional study-specific rules).

10.1.1. Handling of missing data

CCI

CCI

10.1.2. Data derivation

10.1.2.1. Age at vaccination in days

When age at vaccination is to be displayed in days, it will be calculated as:

Age = date of vaccination minus date of birth

10.1.2.2. Age at vaccination in months

When age at vaccination is to be displayed in months, it will be calculated as the number of complete calendar months between the date of birth (DOB) and the date of vaccination. For example:

DOB = 10JUN2017, Date of vaccination = 09JUL2018 -> Age = 12 months

DOB = 10JUN2017, Date of vaccination = 10JUL2018 -> Age = 13 months

10.1.2.3. Age at vaccination in years

When age at vaccination is to be displayed in years, it will be calculated as the number of complete calendar years between the date of birth and the date of vaccination. For example:

DOB = 10SEP1983, Date of vaccination = 09SEP2018 -> Age = 34 years

DOB = 10SEP1983, Date of vaccination = 10SEP2018 -> Age = 35 years

10.1.2.4. Weight

Weight will be presented in kilograms or grams. Weights reported in pounds will be converted as follows:

$$\text{Weight in kilograms} = \text{Weight in pounds} / 2.2$$

$$\text{Weight in grams} = (\text{Weight in pound} / 2.2) \cdot 1000$$

10.1.2.5. Height/Length

Height/Length will be presented in centimeters. Heights/Lengths reported in feet and inches will be converted as follows:

$$\text{Height/Length in centimeters} = \text{Height/Length in inches} \times 2.54$$

10.1.2.6. Body mass index (BMI)

BMI will be calculated as follows:

$$\text{BMI} = (\text{Weight in kilograms}) / (\text{Height in meters})^2$$

10.1.2.7. Temperature

Temperatures will be presented in degrees Celsius (°C). Temperatures reported in degrees Fahrenheit (°F) will be converted as follows:

$$\text{Temperature (Celsius)} = ((\text{Temperature (Fahrenheit)} - 32) \times 5) / 9$$

10.1.2.8. Numerical serology results

Numerical serology results will be derived from the content of IS.ISORRES in the SDTM dataset. For assays with a specific cut-off, the following derivation rules apply:

IS.ISORRES	Derived value
“NEG”, “-“, or “(-)”	cut-off/2
“POS”, “+”, or “(+)”	cut-off
“< value” and value is <= assay cut-off	cut-off/2
“< value” and value is > assay cut-off	Value
“> value” and value is < assay cut-off	cut-off/2
“> value” and value is >= assay cut-off	Value
“value” and value is < cut-off	cut-off/2
“value” and value is >= cut-off	Value
All other cases	Missing

10.1.2.9. Geometric mean titres (GMTs) and concentrations (GMCs)

Geometric Mean Titre (GMT) or Concentration (GMC) calculations are performed by taking the inverse logarithm of the mean of the log titre or concentration transformations. Non quantifiable antibody titres or concentrations will be converted as described in

section 10.1.2.8 for the purpose of GMT/GMC calculation. Cut-off values are defined by the laboratory before the analysis.

10.1.2.10. Onset day

The onset day for an event (e.g. AE, medication, vaccination) is the number of days between study vaccination and the start date of the event. This is 1 for an event occurring on the same day as vaccination (and reported as starting after vaccination).

The onset day for an event (e.g. neonatal AEs, SAEs, AEs of special interest) for infants is the number of days between birth and the start date of the event (or date of diagnosis). This is 1 for an event occurring on the same day as birth.

10.1.2.11. Duration of events

The duration of an event with a start and end date will be the number of days between the start and end dates plus one day, i.e. an event that starts on 03MAR2018 and ends on 12MAR2018 has a duration of 10 days.

The duration of solicited events will be calculated as the sum of the individual days with the adverse event reported at grade 1 or higher during the solicited adverse event period.

10.1.2.12. Counting rules for combining solicited and unsolicited adverse events

For output combining solicited and unsolicited adverse events, all serious adverse events will be considered systemic events since the administration site flag is not included in the expedited adverse event CRF pages. Unsolicited adverse events with missing administration site flag will also be considered systemic.

Multiple events with the same preferred term which start on the same day are counted as only one occurrence.

10.1.2.13. Counting rules for occurrences of solicited adverse events

When the occurrences of solicited adverse events are summarized, each event recorded as having occurred during a specific period will be counted as only one occurrence regardless of the number of days on which it occurs. Also, in the case of co-administered study vaccines, an injection site reaction recorded for a participant following multiple vaccines will be counted as only one occurrence.

10.1.3. Display of decimals

10.1.3.1. Percentages

Percentages and their corresponding confidence limits will be displayed with one decimal except for 100% in which case no decimal will be displayed.

10.1.3.2. Differences in percentages

Differences in percentages and their corresponding confidence limits will be displayed with two decimals.

10.1.3.3. Demographic/baseline characteristics statistics

The mean, median, and standard deviation for continuous baseline characteristics (height, weight, body mass index (BMI), pre-vaccination body temperature) will be presented with one decimal.

The minimum and maximum values and quartile values (if required) will be presented with the same number of decimals as the observed values.

The maxima and minima of transformed height/length/weight variables will be displayed without decimals, with the exception of infant studies where three decimals will be displayed for transformed birth weight.

The maximum and minimum of transformed body temperatures will be displayed with one decimal.

10.1.3.4. Serological summary statistics

The number of decimals used when displaying geometric mean titers (GMT) or concentrations (GMC) and their confidence limits is assay specific based on the magnitude of the assay result post-dose and the clinically relevant assay threshold. The same number of decimals will be used for a given assay regardless of the timepoint presented.

Lowest clinically relevant threshold	Example	Number of decimals to display
<0.3	Diphtheria, tetanus, anti-PRP	3
>=0.3 and <4	Streptococcus pneumoniae , Meningococcal bactericide	2
>=4 and <1000	Measles, rubella, varicella, polio	1
>=1000	CMI	0

GMT/GMC fold increase from pre-dose follows the same principle. Namely when the lowest clinically relevant threshold is 2 fold, 2 decimals are displayed while when the lowest clinically relevant threshold is 4 fold, 1 decimal is displayed.

GMT or GMC group ratios and their confidence limits will be displayed with 2 decimals regardless of the actual values.

10.1.4. Statistical methodology

10.1.4.1. Exact confidence intervals around proportions

The exact confidence intervals around within-group proportions are derived using the method of Clopper and Pearson [[Clopper, 1934](#)].

10.1.4.2. Standardized asymptotic confidence intervals around differences in proportions

The standardized asymptotic confidence intervals around differences in proportions are derived using the method of Miettinen and Nurminen [[Miettinen, 1985](#)]

10.1.4.3. Adjusted GMT or GMC ratios

The CI for GMC ratio and adjusted CMT will be obtained using an ANOVA model on the logarithm transformed titers. The ANOVA model will include the vaccine group as the fixed effect (3 groups) and the country effect. The GMC ratio and their 95% CI will be derived by exponential transformation of the corresponding group contrast in the model.

When between-group GMT or GMC ratios are computed and adjusted for two-level categorical co-variables, these co-variables should be included as dummy continuous variables in the SAS procedure. It should also be clear whether the model is limited to the data from some groups.

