## 4. STUDY DESIGN

### 4.1. Overall design

The study is a Phase III, double-blind, randomized, placebo controlled, multi-centric, multi-country study with 2 parallel groups. At least 20% of participants will be enrolled at centers in the U.S.

The study design is adaptive, with recruitment and randomization occurring in 2 sequential stages, A and B. Stage B may begin immediately after the last participant is randomized in Stage A.

To encourage participation in the study and to achieve recruitment targets on time, the study sites will be encouraged to manage recruitment plans using methods that are acceptable within local regulations such as advertisements in news media and/or use of posters and fliers. All such recruitment materials will be approved by the local ethics committees.

Following verification that inclusion/exclusion criteria are met, all maternal participants will be randomized 2:1 to receive either GSK Biologicals’ RSV Maternal (RSVPreF3) vaccine or the placebo control.

Study procedures in Stage A differ from those in Stage B in 2 ways.

[figure not shown]
During Stage A only:

- All maternal participants will be asked to report solicited events during the 7 days post-dose, and
- Maternal and (as yet unborn) infant participants will be further randomized into sub-cohorts for blood sample collection for the assessment of immune response.

Figure 1 and Figure 2 provide overviews of the study design for maternal and infant participants, respectively.

Section 1.3 provides Schedules of Activities (SoAs) for maternal and infant participants. Section 9.5.1 describes the sequence of analyses for maternal and infant participant data.

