- Randomized intervention allocation: A minimum of 4600 and up to a maximum of 10,000 pregnant women (maternal participants) will be randomly assigned (2:1) to receive the investigational vaccine or control (placebo) at Visit 1. Randomization will take place in 2 sequential stages, A and B. Approximately 4,600 maternal participants will be randomized into Stage A. Stage B will only start after the last participant is randomized in Stage A. Participants in stage A will be randomized (12:2:2:2:6:1:1:1 ratio) to be in the RSV group, in one of the 3 infant blood sampling sub-cohorts and receiving the investigational vaccine (RSVMAT_BS1 (Day 43), RSVMAT_BS2 (Day 121), RSVMAT_BS3 (Day 181)), in the Control group, or in one of the 3 infant blood sampling sub-cohorts receiving placebo (Control_BS1 (Day 43), Control_BS2 (Day 121), Control_BS3 (Day 181)). Randomization will be via the automated internet-based system (SBIR). The system's randomisation algorithm of maternal enrolment will use a minimisation procedure accounting for maternal age at the time of the study intervention (18-34, 35-39, ≥ 40 years of age), gestational age at the time of the study intervention ($24^{0/7}$ - $28^{0/7}$; $28^{1/7}$ - $34^{0/7}$), and center. Minimisation factors will have equal weight in the minimisation algorithm.
- Study (intervention) groups are described in [Table 2](#) and [Table 3](#)
- Data collection: standardized Electronic Case Report Form (eCRF). E-Diaries will be used to collect solicited event data.

- Safety monitoring will be conducted by an unblinded Independent Data Monitoring Committee (IDMC) and by an unblinded Safety Review Team*. The analyses for IDMC safety evaluations will be described in a separate SAP for IDMC.

** Due to the safety signal observed, the study was fully unblinded to ensure the safety of the participants.*

CONFIDENTIAL

212171 (RSV MAT-009)
Statistical Analysis Plan Amendment 5

Table 2 Study groups, sub-cohorts, interventions, and blinding foreseen in the study: Stage A

Approximately 4,600 maternal participants will be randomized during Stage A.

Study groups	Maternal participants (M)				Infant participants (I)			Study Groups for Randomization	Blinding			
	~Number	Age in Years (Min/Max)	Intervention name	Maternal Blood Sampling Sub-cohorts	Infant Blood Sampling sub-cohorts	(Allocation 12:2:2:2:6:1:1:1)	Screening		M only	M + I	I only	
				Name	~Number	Name	~Number					

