8. CHANGES FROM PLANNED ANALYSES

- By-participant listings of SAEs, AEs leading to study withdrawal, MAEs, adverse pregnancy outcomes and pregnancy related AESIs will be prepared and released. Such listings have already been released in earlier analyses. Due to study enrolment/vaccination stop, the study has been unblinded already before the final analysis.
- A sensitivity analysis for immunogenicity results excluding participants from Bangladesh, for which HIV testing was not performed before their enrollment into the study, has been added.
- Between group evaluations for immunogenicity analysis was clarified to be performed among RSV MAT and Control instead of vaccination groups, the wording has been corrected.
- In February 2022, enrollment and vaccination were stopped because of an imbalance in preterm births and associated neonatal deaths observed between the RSVPreF3-Mat and placebo groups. Subsequently the study was unblinded, and therefore the presented VE endpoints are descriptive.
- Subgroup analyses by economic region (LMIC and HIC) will be performed for demography, efficacy, and safety evaluations.
- Subgroup analyses by gestational age at birth will be performed for demography and safety evaluations.
- Sensitivity analysis for primary efficacy endpoints by using a negative binominal regression model have been removed.

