9.2. Immunogenicity

For a given participant and given immunogenicity measurement, missing or non-evaluable measurements will not be replaced. Therefore, an analysis will exclude participants with missing or non-evaluable measurements.

- For the within-group assessment, the descriptive analysis performed for each assay at each timepoint will exclude participants with a missing or non-evaluable measurement.
- For the between group assessments, statistical model will be fitted based on the participants having a result at both the baseline and the considered timepoint.

The GMT/GMC and its 95% CI will be obtained by exponentiating the mean and its 95% CI of the log-transformed titres/concentrations. All CI computed will be two-sided 95% CI.

Placental transfer is defined as the ratio of RSVPreF3 IgG-specific antibody concentrations between cord blood (or blood sample from infants collected within 3 days after birth if cord blood is not available) and maternal blood sample at delivery (or within 3 days after delivery if blood sample is not collected during delivery).

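### The visible GMT/GMC ratio model in the SAP counts three vaccine groups in a two-arm trial, and does not fit the SAP's own baseline-result rule or the IgG testing plan

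*SAP*

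**What the plan says.** SAP 10.1.4.3 gives the only between-group immunogenicity model that can be read in the public text: "The CI for GMC ratio and adjusted CMT will be obtained using an ANOVA model on the logarithm transformed titers". Its terms follow: "The ANOVA model will include the vaccine group as the fixed effect (3 groups) and the country effect". The rest of that section is general. It says how covariates are coded when ratios are "adjusted for two-level categorical co-variables, these co-variables should be included as dummy continuous variables in the SAS procedure", and asks that any limitation of the model to certain groups be made clear.

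Four other places bear on this.

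- **Design.** Protocol 4.1: "The study is a Phase III, double-blind, randomized, placebo controlled, multi-centric, multi-country study with 2 parallel groups".
- **Comparison.** SAP section 8: "Between group evaluations for immunogenicity analysis was clarified to be performed among RSV MAT and Control instead of vaccination groups, the wording has been corrected".
- **Population.** SAP 9.2, for between-group assessments: "statistical model will be fitted based on the participants having a result at both the baseline and the considered timepoint". Within-group summaries need only the measurement at that timepoint.
- **Assays.** SAP Table 1 has maternal RSV-A neutralising titres measured at Day 1, Day 31 and delivery. RSVPreF3 IgG is measured only at delivery and in cord blood, or in an early infant sample if there is no cord blood. The summary of changes for Protocol Amendment 5 and Protocol Table 16 agree.

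SAP 9.3 refers to section 5.3 for the study-specific immunogenicity methods. The body of 5.3.2.2, on the between-group analysis, is redacted.

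**The concern.** An analyst working from the readable text meets three conflicts. The group factor has one more level than the trial has arms, although section 8 reports that the wording on this comparison was corrected. The model uses group and country only, yet it is fitted only in participants who have a baseline result. And the same baseline rule is stated for an assay that no longer has a baseline.

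The second conflict could cost information. Protocol 4.3 says that nearly all adults have had RSV before and that one dose boosts antibody they already carry, so the Day 1 titre should predict the later titre. Requiring a Day 1 result without using it loses participants and gains no precision. Participants are already limited: only maternal-infant pairs are analysed, and SAP 5.3.1 reports that RSV-A neutralisation testing was paused with some samples untested.

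In a study that has been unblinded, choices left to the analyst are better settled in writing before the final immunogenicity analysis.

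**Working it through.** **1. Does any reading give three vaccine groups?**

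SAP section 3 gives the Stage A allocation: "Participants in stage A will be randomized (12:2:2:2:6:1:1:1 ratio) to be in the RSV group", and so on over eight cells.

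- Vaccine cells: 12 + 2 + 2 + 2 = 18. Control cells: 6 + 1 + 1 + 1 = 9. Total 27, and 18:9 = 2:1.
- Arms: 4600 × 18/27 = 3066.7 and 4600 × 9/27 = 1533.3. SAP Table 2 has about 3067 and 1533.
- Immunogenicity sub-cohort: 4600 × 6/27 = 1022.2 and 4600 × 3/27 = 511.1. SAP Table 2 has about 1020 and 510.

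The plan's own numbers are reproduced with two arms. The possible counts are 2 study groups, 8 randomisation cells, and 3 infant blood-sampling cohorts within each arm. The last are sampling times (Day 43, Day 121, Day 181), not vaccine groups. No reading yields three vaccine groups.

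**2. Does the extra level change the estimate?**

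No. If the data hold only RSV MAT and Control, a third level is empty and the contrast between the two real groups is the same.

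**3. Visible model against the baseline rule, by assay.**

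| Assay and sample | Day 1 result in the same person? | Effect of 9.2 on a between-group model |
|---|---|---|
| Maternal RSV-A, Day 31 and delivery | Yes | Participants without a Day 1 result are dropped; 10.1.4.3 names no baseline term |
| Maternal RSVPreF3 IgG, delivery | No | Read literally, nobody qualifies |
| Cord RSVPreF3 IgG | No | Read literally, nobody qualifies |
| Cord and infant RSV-A | No sample from the infant before maternal vaccination; the mother's Day 1 titre exists | 9.2 does not say what counts as baseline |

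**4. What could baseline adjustment be worth?**

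The documents give no titre SD and no correlation between Day 1 and later titres, so the correlation r (on the log scale, within group) is assumed. Adjusting for a covariate with correlation r multiplies the CI width on the log scale by about √(1 − r²), which is equivalent to multiplying the sample size by 1/(1 − r²).

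| Assumed r | √(1 − r²) | CI narrower by | 1/(1 − r²) |
|---|---|---|---|
| 0.3 | √0.91 = 0.954 | 5% | 1.10 |
| 0.5 | √0.75 = 0.866 | 13% | 1.33 |
| 0.7 | √0.51 = 0.714 | 29% | 1.96 |

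These gains apply to maternal RSV-A titres, and only if the model actually run leaves baseline out.

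**The case against.** The best defence is the redaction. SAP 9.3 places the study-specific methods in section 5.3, and 10.1 is introduced as the company's standard rules. The working model may well be in 5.3.2.2, and the restriction in 9.2 is what one would write if baseline were already a covariate. 10.1.4.3 also allows for further covariates. Beyond that, SAP section 6 makes all comparative analyses descriptive, and covariates would be settled after unblinding.

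Much of this stands, and it rules out several stronger readings that a reader might infer.

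- *The plan omits baseline.* Not shown. Only the visible wording of 10.1.4.3 lacks it.
- *10.1.4.3 contradicts 5.3.2.2.* Not shown, because 5.3.2.2 cannot be read.
- *The model cannot be fitted, or estimates the wrong contrast.* Not supported; see step 2 of the working.
- *Every analysed participant needs a baseline result.* Too broad. The rule in 9.2 covers between-group models only.
- *Leaving out maternal age and gestational age at vaccination is an error.* They are minimisation factors, and adding them is reasonable, but the documents do not require it and the redacted model may include them.

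The defence does not remove the visible conflicts. The introduction to 10.1 says its rules are applied together with those of section 9, so 10.1.4.3 is in force. A fixed effect for a stated number of groups plus country is a specific instruction, and its count is wrong for this trial. The redaction also does not explain how 9.2 is meant to work for IgG.

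**Conclusion.** The point holds for the visible text. The group count in 10.1.4.3 is wrong: three stated, two in the trial. The readable model and the baseline rule in 9.2 do not fit each other, and 9.2 read literally leaves no participants for any between-group IgG ratio. IgG is the only assay in the SAP's secondary endpoints that is reported as a concentration, so the GMC wording in 10.1.4.3 most naturally refers to it.

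The consequence is an inconsistent specification with a possible loss of precision for maternal RSV-A titres. At r = 0.3 to 0.7 the CI would be 5% to 29% wider-than-needed in the sense that adjustment would narrow it by that much. This rests on an assumed r and on baseline being absent from the model actually used. The number of participants lost for want of a Day 1 result cannot be computed; Day 1 blood was planned for all mothers, so it may be small. No bias is demonstrated. The analysis is secondary and descriptive, and no alpha, power or success criterion depends on it.

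**What to change.** 1. In SAP 10.1.4.3, replace the three-group wording with the two groups RSV MAT and Control, in line with section 8.
2. For maternal RSV-A neutralising titres at Day 31 and delivery, state that log Day 1 titre is a covariate alongside group and country. This agrees with the restriction in 9.2.
3. For RSVPreF3 IgG, use the model without baseline and say that the baseline-result requirement in 9.2 does not apply.
4. Check 10.1.4.3 and 9.2 against 5.3.2.2 so that all three describe one model for each assay and timepoint.

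Optional: add maternal age group and gestational age at vaccination, and use the mother's Day 1 titre as baseline for cord and infant RSV-A titres. If the mother's titre is not used there, say that the baseline requirement does not apply to those samples either.

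The cost is SAP wording and a small program change, with no new data. The drawback is that covariates are being stated after unblinding. The change should therefore be dated and given its reason in SAP section 8; if 5.3.2.2 already contains this model, only the wording of 10.1.4.3 and 9.2 needs to change.
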